4.13 Treatment Compliance

Template: WCT-TP-ST-005-005 Page 15 of 24 Effective Date: 15-Apr-2016 Confidential

A participant is considered compliant with the study protocol when study medication is administered at a compliance level of ≥80% (excluding dose holds for surgical operations or drugrelated AEs). Treatment compliance will be calculated overall as follows:

(Total [cumulative] amount of treatment actually taken [mg])/Total [cumulative] amount of treatment that should have been taken [mg]) x 100

The total (cumulative) amount of treatment actually taken (mg) will be calculated as described in Section 4.12. The total (cumulative) amount of treatment that should have been taken (mg) will be calculated for each dose strength received as dose strength * (end date at that dose level – start date at that dose level) + 1 day, summed across all dosing records available for a participant.

Compliance will be summarized by Part, Cohort, and overall using the Safety Population. A listing of this data will also be provided.

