## **6.6** Treatment Compliance

A participant is considered compliant with the study protocol when study medication is administered at a compliance level of  $\geq 80\%$  (excluding dose holds for surgical operations or drug-related AEs).

Compliance will be calculated using the following equation:

([Number of capsules ingested] / [Number of capsules that should have been ingested]) \*100%

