4.3.4 Exposure to Study Drug

Exposure to miransertib will be calculated as follows: date of last dosing minus the first day of dosing + 1. The exposure calculation will not take into account breaks in therapy.

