7 CHANGES TO PLANNED PROTOCOL ANALYSIS

General changes:

Under Protocol Amendment 7, the primary study objective for both Part A and Part B was updated to describe the safety and tolerability of miransertib in patients with PROS and PS, and further efficacy assessments were removed. Part A was closed to enrollment after the approval of Amendment 6. Amendment 7 will complete the final enrollment into the MOSAIC study and Compassionate Use/Expanded Access Program. In the future, patients will be transitioned to new miransertib programs.

Specific changes:

Protocol section 6.6 states that study drug compliance is to be calculated using the following formula:

• ([Number of capsules ingested] / [Number of capsules that should have been ingested])*100%.

Template: WCT-TP-ST-005-005 Page 21 of 24 Effective Date: 15-Apr-2016 Confidential

Compliance is unable to be calculated using this formula. Subjects have the option of being administered capsules as either 5mg or 10mg, and it is not possible to determine from the data collected on the eCRF the actual number of capsules that should have been ingested. Because of this, an alternative method to calculate compliance has been specified in this SAP.

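### The SAP 4.13 compliance denominator adds a day to milligrams and has no term for the dose holds its own definition excludes; the two errors pull in opposite directions

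*SAP*

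**What the plan says.** Protocol 6.6 defines compliance as capsules ingested over capsules that should have been ingested. It sets the threshold at 80%, "excluding dose holds for surgical operations or drug-related AEs". SAP section 7 explains that the eCRF data cannot supply the expected capsule count, because participants may receive 5 mg or 10 mg capsules, and that therefore "an alternative method to calculate compliance has been specified in this SAP".

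That method is in SAP 4.13. It keeps the 80% threshold and the exclusion of holds, and works in milligrams. For the numerator, "The total (cumulative) amount of treatment actually taken (mg) will be calculated as described in Section 4.12", that is, from capsule counts. The denominator is the amount that should have been taken, also in mg: dose strength times (end date minus "start date at that dose level) + 1 day, summed across all dosing records available for a participant".

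For exposure, SAP 4.3.4 counts days inclusively: "date of last dosing minus the first day of dosing + 1". Both 4.3.4 and 4.12 say that breaks in therapy are ignored when duration of exposure is calculated.

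**The concern.** There are two separate faults in one line.

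- **Units and bracket.** By normal operator order the dose multiplies only the date difference. The additional day is then added to a quantity in milligrams, once per record. Nearly a full day's dose is lost from the denominator of each record, and the ratio rises.
- **Holds.** The section says that holds for surgery and drug-related adverse events do not count against the participant, but the formula removes nothing. If a hold lies inside a dosing record, its days stay in the denominator and the ratio falls. Nothing else in the SAP tells a programmer to subtract them, and the exposure rules nearby deliberately ignore interruptions.

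At stake is the compliant/non-compliant label, which is summarised by Part, Cohort and overall. This is the only operative rule for it. The planned Part B cohorts have about 10 to 25 participants each, so one or two wrong labels would be visible in a percentage.

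**Working it through.** The plan gives no worked compliance figure, so there is nothing to reproduce.

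**Inputs from the documents.** Daily doses run from 5 to 45 mg (Protocol Appendix 2). A cycle is 28 days and treatment lasts up to 48 cycles, so 48 × 28 = 1344 days. Drug is dispensed monthly at C1–C4, two-monthly at C5, C7, C9 and C11, three-monthly at the 11 visits from C13 to C43, and two-monthly at C46 (Protocol Table 3). A toxicity hold may last up to 21 days before restart (Protocol 6.5). Major surgery requires at least 2 weeks off before and 1 week after, also 21 days (Protocol 6.8.1).

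**Assumed.** The number and length of dosing records; also that a record's end date is the last day at that dose.

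**Step 1: one record of L inclusive days at D mg**

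- As written: D(L−1) + 1. Inclusive: D×L. Shortfall: D − 1 mg.
- The shortfall is 4 mg at 5 mg/day (0.80 of a day's dose), 24 mg at 25 mg/day (0.96) and 44 mg at 45 mg/day (0.98). It is positive at every dose in the nomogram.
- Compliance is multiplied by D×L / [D(L−1) + 1].

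**Step 2: effect over a participant's records**

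| Assumed records | Inclusive mg | As written mg | Factor | True value that reads 80% |
|---|---|---|---|---|
| Two: 15 mg × 84 d, 25 mg × 1260 d | 32,760 | 32,722 | 1.001 | 79.9% |
| One per dispensing visit (20), 25 mg, last one 84 d | 33,600 | 33,120 | 1.014 | 78.9% |
| Same, last one 56 d | 32,900 | 32,420 | 1.015 | 78.8% |
| 28 days each, 25 mg (per record) | 700 | 676 | 1.036 | 77.3% |

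In the second and third rows the shortfall is 20 × 24 = 480 mg.

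**Step 3: if one record's end date equals the next record's start date**

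Take 48 records of 28 days at 25 mg (33,600 mg in truth). The first 47 have an end-minus-start of 28 and the last has 27.

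- As written: 47 × 701 + 676 = 33,623 mg, factor 0.999. The error all but disappears.
- Bracket moved and nothing else done: 47 × 725 + 700 = 34,775 mg, factor 0.966. Each boundary day is now counted twice.

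**Step 4: a hold left in the denominator**

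Take a 21-day hold inside an 84-day record at 25 mg, with every other dose taken.

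- Taken: 63 × 25 = 1575 mg.
- As written: 1575 / (25 × 83 + 1) = 1575 / 2076 = 75.9%.
- Bracket corrected: 1575 / 2100 = 75.0%.
- With the bracket corrected, (T − 21)/T < 0.80 only when T < 105 days. At T = 336 days the figure is 315/336 = 93.8%.

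**The case against.** The intent is hardly in doubt. A term labelled as a day can belong only to the date difference, and the SAP counts inclusive days for exposure. A programmer following 4.3.4 would probably code it correctly. Punctuation in this copy of the SAP is also unreliable: the minus signs in 4.2.3 and 4.12 are missing. Against that, the brackets in the denominator expression are balanced, so a lost bracket is not the obvious explanation. The text should not depend on silent correction.

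The hold exclusion is stated just before the formula, and it could be read as an instruction to remove those days. Also, under Protocol Table 6 a Grade 3–4 toxicity that recovers in time restarts at a lower level, so that hold may fall between dose-level records. Both arguments narrow the gap. They leave open holds followed by a restart at the same dose, which Table 6 provides for after Grade 2 toxicity and which can also follow surgery.

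A reader might infer that reported compliance is simply overstated. The documents do not support that: the hold error runs the other way, and shared record dates would remove most of the bracket error. A reader might also work out much larger inflation for records of 7 or 14 days. No schedule in the protocol produces such records routinely, and compliance is calculated over all records together, so an occasional short one has little effect.

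**Conclusion.** The point holds for the formula as written, and it is minor. The units do not match, the line disagrees with SAP 4.3.4, and an exclusion stated in the same section has no counterpart in the calculation. If end dates are last dosing days, the bracket error inflates compliance by about 0.1% to 3.6% in relative terms, depending on a record structure the documents do not describe. An unsubtracted hold lowers compliance, and can take a fully adherent participant below 80% when total time on treatment is short. The net direction is not fixed.

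The bracket error alone can relabel only participants just under 80%. Compliance is descriptive: the Safety Population requires only one dose, the endpoints are adverse event frequency, duration and severity, and no analysis set depends on the label.

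**What to change.** Rewrite the denominator in SAP 4.13 as the sum over records of assigned daily dose (mg) × (end date − start date + 1), minus daily dose × days on hold for surgery or drug-related adverse events where the hold lies inside a record. Add two clarifications:

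- Where one record's end date equals the next record's start date, the shared day is counted once. Step 3 shows why moving the bracket alone is not enough.
- The dose in the formula is the assigned daily dose, not the capsule strength.

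The cost is about one line of SAP text and slightly changed compliance figures. Hold dates must be identifiable in the dosing data; the documents do not show how the eCRF records them, so this should be checked first.

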4.14 Pharmacokinetic Analyses (Part A and B)

Pharmacokinetic analyses will be analyzed and reported in a separate report.

4.15 Safety Analyses

All participants who receive at least one dose of study treatment will be evaluated for safety.

Safety and tolerability will be assessed by clinical review of all relevant parameters including AEs, SAEs, 12-lead electrocardiogram (ECGs), physical examination, vital signs, and clinical laboratory tests.

Descriptive summary statistics such as counts and percentages will be provided for safety analysis.

Exploratory analyses will also be performed on other safety parameters, as deemed appropriate,

within subgroups defined by age at enrollment (<12 years, ≥12 to <18 years, ≥18 years) and disease (PROS, PS). Further details regarding these subgroup analyses are provided in the following sections. concomitant use of pain relief medications. Age subgroups to be considered will be less than 5, 5 to 7; 8 to 11; 12 to 18 subject to number of patients available within each of these

Template: WCT-TP-ST-005-005 Page 16 of 24
Effective Date: 15-Apr-2016 Confidential

groups. Where an age group category has less than 5 patients then this category will be merged with the previous one.

4.16 Adverse Events

AEs will be assessed by the frequency, duration and severity from the first dose of miransertib through 90 days after the last dose of the drug. Severity of AEs will be assessed by the current version of Common Terminology Criteria for Adverse Events (CTCAE). A treatment emergent adverse event (TEAE) is defined as follows:

- Any AE that has an onset on or after the first dose of study drug and before last dose of study drug + 90 days.
- Any pre-existing AE that has worsened in severity on or after the first dose of study drug and before the last dose of study drug + 90 days.

A treatment-related AE (TRAE) is defined as an AE as being related to miransertib.

The following tables will be presented for AEs:

- Overall incidence and the number of TEAEs, ≥ grade 3 TEAEs, serious AEs (SAEs), TRAEs, serious TRAEs, TEAEs leading to early study withdrawal, and deaths (TEAEs leading to death and AEs leading to death).
- TEAEs by SOC and PT, incidence and number of events
- TRAEs by SOC and PT, incidence and number of events
- Serious TEAEs by SOC and PT, incidence and number of events
- Serious TRAEs by SOC and PT, incidence and number of events
- Serious TRAEs resulting in death by SOC and PT, incidence and number of events
- Serious non-TRAEs by SOC and PT, incidence and number of events
- Non-serious TEAEs by SOC and PT, incidence and number of events
- Non-serious TEAEs by SOC and PT, incidence >5% in one or more cohorts and number of events
- TEAEs by SOC, PT, and maximum toxicity, incidence
- TEAEs leading to early study withdrawal by SOC and PT, incidence
- TEAEs reported in ≥10% of participants by PT, sorted by decreasing incidence of PT

Template: WCT-TP-ST-005-005 Page 17 of 24 Effective Date: 15-Apr-2016 Confidential

- TRAEs reported in ≥10% of participants by PT, sorted by decreasing incidence of PT
- Serious TEAEs reported in ≥5% of participants by PT, sorted by decreasing incidence of PT
- All AEs resulting in death by PT, sorted by decreasing incidence of PT
- Listing of TEAEs
- Listing of SAEs
- Listing of TEAEs leading to early study withdrawal
- Listing of subjects with TEAEs resulting in treatment interruption
- Listing of subjects with TEAEs resulting in treatment discontinuation
- Listing of AEs leading to death

In counting the number of AEs reported, a continuous event (i.e. reported more than once and which did not cease), will be counted only once; non-continuous AE reported several times by the same subject will be counted as multiple events.

Additionally, the following tables will be produced by grade (<3, ≥3) and separately by the subgroups of age at enrollment (<12 years, ≥12 to <18 years, ≥18 years) and disease (PROS, PS):

- TEAEs by SOC and PT, incidence and number of events
- TRAEs by SOC and PT, incidence and number of events; overall and separately by grade category (<3, ≥3)
- Serious TEAEs by SOC and PT, incidence and number of events; overall and separately by grade category (<3, ≥3)
- Serious TRAEs by SOC and PT, incidence and number of events; overall and separately by grade category (<3, ≥3)
- Serious non-TRAEs by SOC and PT, incidence and number of events; overall and separately by grade category (<3, ≥3)

TEAE duration by SOC and PT:

The duration of each AE for each participant will be calculated in days by subtracting the date of the start of the AE from the date of the end of the AE + 1 day. The AE duration will be summarized in the AE listings.

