#### 4.2.1 Discontinuation From Treatment

- Participant experiences, in the opinion of the investigator, an acceleration of the overgrowth disease.
- Miransertib-related clinically significant toxicities that do not recover despite optimal treatment or dose reduction.
- Participant needs to take or elects to take another investigational agent.

• Development of any concurrent medical condition that might preclude or

contraindicate the further administration of miransertib.

- Serious protocol violations such as noncompliance with treatment or required follow-up and evaluation as determined by the investigator.
- Investigator's decision (in agreement with the Sponsor's Medical Monitor or designee).
- Participant, or guardian, refusal of further treatment/withdrawal of consent. Reasons for refusal of further treatment/withdrawal of consent should be noted in that participant's medical record.
- Death.

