# 4.2.2 Discontinuation From the Study

- Participant and/or guardian refusal of further examinations (follow-up visits) and/or communications with the site/withdrawal of consent. Reasons for refusal/withdrawal of consent should be noted in that participant's medical record.
- Lost to follow-up.
- · Death.

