#### 6.5 Dose Modifications

When a drug-related toxicity is observed, dose interruptions and/or reductions in miransertib administration are allowed. In general, once the dose of miransertib has been modified for a participant, all subsequent doses should be administered to that participant at the modified dose level. A drug-related toxicity is any toxicity considered related, probably related, or possibly related to miransertib.

Dose reduction should occur according to Table 5. Guidelines for dose interruptions for drug-related toxicities and hyperglycemia are detailed in Table 6 and Table 7, respectively.

Table 5 Miransertib Dose Reduction Schedule

Administered Dose	Dose Reduction
25 mg/m  qd:	15 mg/m² qd
	10 mg/m² qd
	5 mg/m  qd
15 mg/m  qd (during first 3 cycles)	10 mg/m² qd
	5 mg/m  qd

qd=once per day

Dose reduction is allowed and should be performed per Table 5. If the dose reduction is indicated, the participant should be assigned to the lower dose and it should be agreed on by the investigator and the Sponsor. Dose re-escalation will not be permitted.

Treatment will be permanently discontinued in case of Grade 2 drug-related toxicity that does not recover within 21 days after holding miransertib, or Grade 3 drug-related toxicity at the lowest dose (5 mg/m²), or if another discontinuation criterion listed in the protocol is met.

Table 6 Dose Interruptions/Reductions for Drug-Related Toxicity Except Hyperglycemia

Event Grade (CTCAE)	Action
Grade 1	Continue current dose level.
Grade 2	Withhold miransertib until recovery to Grade 1 or baseline. If recovery occurs within 21 days of holding miransertib, restart miransertib at the same dose level, unless further dose reduction is required.
	If a participant experienced a Grade 2 drug-related toxicity that does not recover within 21 days of holding miransertib at a higher dose level (25 mg/m  or 15 mg/m  ), they will be allowed to reduce the dose to the next lower level once the event has recovered to Grade 1 or baseline.
Grade 3-4	Withhold miransertib until recovery to Grade 1 or baseline. If recovery occurs within 21 days of holding miransertib, restart miransertib at the next lower dose level for subsequent doses, unless further dose reduction is required.
	If recovery occurs after more than 21 days on drug hold, permanently discontinue miransertib.

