2.1 Study objectives

2.1.1 Primary Objective

The primary study objective for both Part A and Part B is to describe the safety and tolerability of miransertib in patients with PROS and PS.

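### SAP 4.16 tabulates TEAEs leading to an undefined early study withdrawal but only lists TEAEs leading to treatment discontinuation or interruption, so AE-driven drug stops and holds have no tabulated incidence

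*SAP*

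**What the plan says.** The sole objective, in SAP 2.1.1, is to "describe the safety and tolerability of miransertib in patients with PROS and PS". SAP 4.16 handles AE-driven changes to treatment or participation as follows.

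- The overall AE summary has an item for "TEAEs leading to early study withdrawal, and deaths".
- There is a separate table of "TEAEs leading to early study withdrawal by SOC and PT, incidence", and a listing of the same events.
- Stopping the drug gets a "Listing of subjects with TEAEs resulting in treatment discontinuation".
- Holding the drug gets a "Listing of subjects with TEAEs resulting in treatment interruption".
- Dose reduction appears in none of the section's outputs.

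The protocol separates two kinds of exit. Section 4.2.1, on leaving treatment, includes "Miransertib-related clinically significant toxicities that do not recover despite optimal treatment or dose reduction". Section 4.2.2, on leaving the study, has three entries: "Participant and/or guardian refusal of further examinations (follow-up visits) and/or communications with the site/withdrawal of consent", loss to follow-up, and death.

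**The concern.** How often a drug has to be stopped or held because of adverse events is a standard measure of tolerability, and tolerability is half of this study's only objective. The SAP gives an incidence to the exit that the protocol does not link to toxicity. The exit that the protocol does link to toxicity gets listings without a denominator. A reader of the study report will naturally look to the withdrawal row for the rate of stopping due to adverse events. If that row counts only study exits, it can look favourable while participants were stopping or holding miransertib. The proper incidence by preferred term would then have to be counted by hand from listings. SAP 4.15 also commits to counts and percentages for the safety analysis, and a listing does not provide them.

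**Working it through.** No formula or stated figure is involved. The check sets the planned outputs against the protocol's definitions.

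**1. Count of outputs in SAP 4.16**

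| Consequence of the TEAE | Row in overall summary | SOC/PT incidence table | Listing |
|---|---|---|---|
| Early study withdrawal | 1 | 1 | 1 |
| Treatment discontinuation | 0 | 0 | 1 |
| Treatment interruption | 0 | 0 | 1 |
| Dose reduction | 0 | 0 | 0 |

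**2. Where the protocol sends a toxicity stop.** Section 4.2.1 puts unresolved drug-related toxicity under treatment. Section 6.5 also acts on the drug: "Treatment will be permanently discontinued in case of Grade 2 drug-related toxicity that does not recover within 21 days after holding miransertib". Table 6 in the same section gives a different action for that Grade 2 case at the higher dose levels, and the two need reconciling, but both are actions on the drug and neither ends study participation. Section 7.5 then requires at least 30 days of follow-up after the drug is stopped, and Annex 1 schedules end-of-treatment and safety follow-up assessments for Part A after any permanent stop. A participant who stops for toxicity and attends follow-up has therefore met none of the three reasons in 4.2.2.

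**3. Whether the SAP treats the terms as synonyms.** It has one listing for TEAEs leading to study withdrawal and another for TEAEs leading to treatment discontinuation. That suggests two different events, but no definition settles it.

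**4. Whether another output fills the gap**

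- SAP 4.6 tabulates reasons for premature withdrawal. It does not say whether that means withdrawal from treatment or from the study, gives no SOC/PT breakdown, and does not cover holds.
- SAP 4.3.4 and 4.12 compute exposure without regard to breaks, so holds do not show there.
- SAP 4.13 sets aside holds for drug-related AEs in its compliance criterion.
- SAP 4.12 gives the number and percentage of participants who received each dose level. Part B Cohorts 1 to 3 start at 15 mg/m² (protocol 6.3), and Table 5 gives 10 and 5 mg/m² as reduction levels. In those cohorts the output therefore shows who went below the starting dose. It cannot show a step from 25 to 15 mg/m², because everyone there has already taken 15. In Cohort 4 it is ambiguous, because those already on drug continue at their dose at enrolment. It has no link to an AE.

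None of these gives the incidence of AE-driven discontinuation by preferred term, or of AE-driven interruption at all.

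**5. Scale.** Using the planned sizes in SAP 2.3, one participant missed from the tabulated rate is 1/20 = 5.0% of Cohort 1, 1/10 = 10.0% of Cohort 2, 1/25 = 4.0% of Cohort 3, 1/10 = 10.0% of Cohort 4, and 1/65 = 1.5% of Part B. As an illustration that such stops occur, the protocol synopsis reports that 1 of 6 participants in the earlier Proteus syndrome study stopped treatment for a transaminase increase.

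**6. Whether the data exist.** Protocol 7.2 asks sites to record AEs that cause temporary or permanent discontinuation of study medication, and the two planned listings rely on that information. Section 7.2 does not mention dose reduction.

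**The case against.** The best case for the plan has four parts.

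- **The stated endpoint is covered.** SAP 2.2.1 defines safety and tolerability through AE frequency, duration and severity. SAP 4.16 tabulates TEAEs, treatment-related AEs, serious events, Grade 3 or higher events and maximum grade. Protocol 9.4 promises no table of AE-driven discontinuation. This stands. A reader might infer that tolerability has no incidence at all, and the documents do not support that. The gap is confined to AE-attributed discontinuation and interruption.
- **The protocol blurs the two exits.** The sentence that opens section 4.2 covers removal from treatment or from the study under one set of criteria, and death and withdrawal of consent appear in both lists. SAP 4.6 summarises early withdrawals by the dose at the time, which fits stopping the drug. This stands as far as it shows that early study withdrawal might be programmed to include toxicity stops. It also shows why the term needs a definition, since an output for the primary objective should not depend on a programmer's guess.
- **The information is not lost.** Affected participants can be found in the listings, SAP 4 allows extra tables in the study report, and the protocol synopsis describes a narrative summary of safety. This limits the severity. It does not supply a planned incidence.
- **The existing table has its own use.** It shows which events led participants to leave the study. This stands, and it is a reason to add outputs and not to replace that one.

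**Conclusion.** The point holds as a reporting gap that should be closed. If early study withdrawal is read as in protocol 4.2.2, the only tabulated rate of AE-driven exits misses participants who stop miransertib for toxicity but remain for follow-up. Whichever way the term is read, AE-driven interruption has no tabulated incidence. No estimate, test or decision rule changes.

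The size is unknown before data. It depends on how many participants stop for toxicity and stay, and on how the case report form and table shells, which are not in the documents, define withdrawal.

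Two stronger readings are tempting and are not supported. A reader might infer that the withdrawal table will show little beyond deaths. That assumes strict use of 4.2.2 by sites and programmers, and consent withdrawn because of an AE would enter the table as well. A reader might also infer that TEAEs leading to dose reduction could be tabulated from existing data. Dosing records show that a dose level fell, but the documents do not show that the responsible AE is recorded.

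**What to change.** In SAP 4.16:

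1. Add a row to the overall AE summary, and an incidence table by SOC and PT, for TEAEs leading to permanent treatment discontinuation.
2. Add a row to the overall AE summary for TEAEs leading to treatment interruption.
3. Define early study withdrawal in line with protocol 4.2.2 and keep its existing row, table and listing.
4. Report n (%) of participants with any reduction in dose level, taken from the dosing records and defined on the mg/m² level, so that changes in milligrams due to growth are not counted. Attribute a reduction to a TEAE only if the case report form records that link.

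Items 1 and 2 use the data already behind the planned listings, and item 4 uses dosing records that SAP 4.13 already relies on. The cost is one definition and a few extra outputs. These are reporting changes only and alter no treatment rule.
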